STUDY PROTOCOL (Version 1, 1/17/2018)^[L1]_[SEP]

Title: Retinal displacement after scleral buckling (SB) versus scleral buckle combined with vitrectomy (PPV+SB) for the management of primary retinal detachment: ALIGN SB vs. PPV-SB. An extension of the study of “Retinal displacement after pneumatic retinopexy (PnR) versus vitrectomy (PPV) for the management of primary retinal detachment (ALIGN) NCT04089033.”

Principal Investigators:

[name]^[L1]_[SEP]

[name]

Co-investigators:

[name]^[L1]_[SEP]

[name]

[name]

[name]

[name]

[name]

[name]

[name]

Study coordinator:

Setting:

[figure not shown]
I. Background

Retinal detachment^[L1]_[SEP]

Rhegmatogenous retinal detachment (RRD) is an acute, sight threatening condition,

with an incidence of approximately 10 per 100,000 people.¹ During normal ageing, the transparent vitreous gel (see figure 1:A), which fills the eye, liquefies and shrinks, and eventually detaches in 80% of the eyes. When detachment of the gel occurs, a tear in the retina may form (see figure 1:B). Liquified gel may now enter under the retina via the retinal tear (see figure 1:C), resulting in detachment of the retina (see figure 1:D). Once retinal detachment occurs, sight loss usually develops within several hours to days.

Figure 1: Retinal detachment

Factors that predispose an individual to developing retinal detachment are myopia (near sightedness), advancing age, trauma, and certain hereditary conditions.² Without any surgical intervention by a vitreoretinal surgeon, retinal detachment almost invariably results in permanent sight loss in the affected eye. There is an increased risk of delayed visual rehabilitation the longer the wait for surgery is.³ Interventions for rhegmatogenous retinal detachment may include Scleral Buckling (SB), Pneumatic retinopexy (PnR), Pars Plana Vitrectomy (PPV), and PPV+SB in which the primary objectives are to close and seal the retinal break and reattach the neurosensory retina to the RPE.⁴⁻¹⁰ The choice of which procedure to perform depends on the clinical examination and the surgeon's discretion as to which will be best for the patient in that specific scenario.

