Vitrectomy surgery (PPV) involves 'keyhole' surgery to the eyeball, via three tiny (23/25 gauge) incisions to the sclera. This procedure is carried out in the operating room, under regional anaesthetic (a freezing injection to the retro-bulbar space, the space behind the eyeball, where nerves which sense pain and control eye movement are situated) plus sedation (medication to reduce patient anxiety). During PPV, the vitreous gel is removed from the eye using a fine metal instrument called a 'vitrector'. The vitreous gel is removed to allow space for a larger gas bubble than is possible in PnR, and also to relieve any vitreous traction which may otherwise impair reattachment of the retina. A large gas bubble (same gases as mentioned for PnR) is injected (to reattach the retina, as in PnR), and laser or cryotherapy is applied around the retinal tear to secure it (as in PnR). After treatment, a patient may be required to maintain a 'head posture' (for example, head tilt to left) for up to one week. The purpose of this 'head posture' is to support the area of the retinal tear optimally, by 'floating' the gas bubble up against it. As the gas bubble is larger in PPV, the head posturing requirements are less strict. The gas bubble reabsorbs after 2-6 weeks, depending on the gas selected. The surgery takes 1-1.5 hours. The success rate (i.e. the proportion of patients in whom the retina becomes attached after one treatment) is reported as being as high as 90% in the scientific literature.^{7,12,13}

Scleral buckling (SB) is another method used for repair of RD that involves encircling the eye with a silicone band, and may or may not involve the use of a gas bubble. This

has been reported to have better visual results than PPV in phakic patients.¹⁵

Another surgical technique for repair of RD is PPV combined with SB (PPV/SB), and this is used commonly in treatment of larger or more complex detachments. The surgery combines the two techniques, and involves the use of a large and often long-acting gas bubble similar to what is done in PPV surgeries.

All the treatment options may be associated with complications such as bleeding, infection, increased intraocular pressure or cataract. The risk of a sight threatening complication such as a severe intraocular infection or hemorrhage is less than 1:1000. The risk of cataract development (clouding of the lens, requiring cataract extraction surgery) is less in PnR^{11,14} and SB compared to PPV.¹⁵

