Distortion and retinal displacement after retinal detachment repair

Image distortions such as metamorphopsia and micropsia are common complaints after surgery for retinal detachment. In 2010 Shiragami et al were the first to demonstrate hyper-fluorescent lines, adjacent to the retinal blood vessels in Fundus auto-fluorescence imaging (FAF) of the retina after retinal detachment (RD) repair surgery.²⁶ They proposed a theory in which these lines which are called also Retinal Vessel Printing (RVP) correspond to the area where the retinal blood vessels were located before the retinal detachment. According to this theory the RVP in FAF imaging is due to increased metabolic activity of RPE cells. Prior to surgery these RPE cells were obscured to light rays by retinal blood vessels while after surgery, due to displacement of the retina, these RPE cells became exposed to the light which leads to increase in the cells metabolic activity. This increase in metabolism is thought to be the cause for the hyper fluorescence seen in FAF imaging. Displacement of the retina after RD repair surgery can serve as anatomy basis of vision distortion. Moreover, these reference lines allow us to quantify the displacement of the retina after retinal detachment surgeries. By doing this, we can compare retinal displacement of different retinal detachment repair surgeries and may reduce post operation visual distortion.

Since Shiragami's first report, several other studies looked into retinal displacement after RD repair²⁶⁻³², epiretinal membrane³³ and macular hole³⁴. Codenotti et al have shown that retinal displacement ratio is higher in patients with intravitreal gas compare to patients with silicon oil (71.4% vs. 22.2%).²⁷ Lee et al proposed a way of quantifying the rotational displacement of the retina.²⁸ They showed that there is more than a simple rotation and probably also a temporal stretch of the retina. Recently Dell'omo published the biggest study so far of 125 patients after pars plana vitrectomy (PPV) with 35.2% of patient showed signs of retinal displacement.³⁰

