Recently we showed in PIVOT trial that patients after pneumatic retinopexy has less vertical distortion than patients after PPV. To the best of our knowledge, no study so far looked into retinal displacement after Pneumatic Retinopexy. Moreover, wide field FAF was not used in previous studies. We think there is a reason to believe that Pneumatic Retinopexy will cause less retinal displacement than PPV. Thus, we propose a prospective cohort study which will compare retinal displacement of patients after RD repair by PPV versus Pneumatic Retinopexy.

In addition, we wish to include VitreoRetinal Surgery, PA in Minnesota and Bhagwan Mahavir VitreoRetinal Services, Sankara Nethralaya in India as the site to study retinal displacement following RD repair using either SB or PPV with SB, since this practice has a much higher volume of those surgical methods.

II. Aim (SB and PPV+SB arm)

To compare retinal displacement and visual distortion of primary retinal detachment repair following scleral buckling (SB) versus scleral buckle combined with pars plana vitrectomy (PPV+SB).

III. Study design

(i) Hypothesis The primary study hypothesis is that scleral buckling alone may cause less retinal displacement and less visual distortion at the first 12 months for patients with primary retinal detachment than other methods.

(ii) Experimental design A prospective, cohort trial, evaluating scleral buckling alone and scleral buckling combined with vitrectomy outcomes for patients with primary retinal detachment.

(iii) Participants Patients presenting to vitreo-retinal service with rhegmatogenous retinal detachment. Eligibility for study participation will be ascertained by the examining physician at the time of presentation:

Inclusion criteria:

- Age \geq 18
- Diagnosis of macula off primary rhegmatogenous retinal detachment

Exclusion criteria:

- Previous retinal detachment and/or retinal detachment repair surgery in the study eye
- Retinal detachment with macula on.
- Patients with other retinal pathologies causing structural changes to the retina in the study eye, such as diabetic retinopathy, previous vascular occlusion (artery or vein occlusion), macular dystrophy, among others.
- Previous vitreoretinal surgery in the study eye
- Inability to come for follow ups up to 12 months.
- Inability to take FAF imaging due to neck stiffness or other medical issue.
- Inability to maintain post operation head positioning
- Mental incapacity

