- Inability to sign on informed consent.
- Patient is unwilling or unable to follow or comply with all study related procedures or to sign informed consent form

Criteria for participant withdrawal from study: - Patient withdraws consent

(v) Interventions

The only interventions in the study are performed at the 3 and 12 month postoperative visit, and include fundus imaging (FAF and OCT), and sensory testing with the M chart and the Aniseikonia test, as detailed below.

Participants will be chosen from those undergoing either scleral buckling alone or scleral buckling combined with vitrectomy for repair of a macula-off retinal detachment. Patients are not randomized to the procedure, rather the procedure is chosen by the surgeon in the best interests of the patient.

In the event of primary intervention failure (i.e. failure of retinal re-attachment following primary intervention), the decision to proceed with secondary intervention, and the nature of such intervention, will rest with the treating physician in conjunction with the patient. Secondary intervention may involve any surgical procedure, as deemed clinically appropriate.

Note: Additional laser retinopexy, cryotherapy, gas injection or head positioning are not considered a failure.

(vi) Timing of observationsSee flow diagram (Appendix 1)

Imaging

Fundus AutoFluorescence (FAF)

Fundus autofluorescence (FAF) imaging is a noninvasive imaging method and requires relatively little time. It highlights the fluorophores accumulating in lipofuscin (LF) within retinal pigment epithelium cells (RPE). No radiation is involved therefore this imaging method is safe without any clear contraindications.

M Chart

Recently, several tools have been developed for quantification of metamorphopsia severity including M-CHARTS (Inami Co., Tokyo, Japan). In the patients with metamorphopsia, a straight line appeared curved or irregular. On M-CHARTS, straight lines are replaced with dotted lines, and the dot intervals (range: 0.2° - 2.0°) are changed from fine to coarse. With increasing dot interval, the line distortion decreases until the dotted line becomes straight. The visual angle that denoted the dot interval of the line seen as straight was considered as the patient's M-CHARTS score. When a

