patient was tested with vertical dotted lines, the result was defined as the vertical M-CHARTS score. After the M-CHARTS were rotated 90°, the horizontal M-CHARTS score also was measured according to horizontal dotted lines³⁵.

Aniseikonia test

Aniseikonia is a phenomenon in which the size or shape of perceived images differs between eyes. The anomaly is reported to be associated with interocular differences in refractive error and some retinal diseases. Following successful repair for rhegmatogenous retinal detachment, some patients have complained that objects appeared distorted in size or shape. The Aniseikonia Test measures the ratio of image size difference between the 2 eyes³⁶.

(vii) Outcome measures^[11]_[SEP]

Primary outcome:

- retinal displacement by the presence of retinal vessels printing on FAF imaging.

Secondary outcome:

- Visual Distortion measured with M chart.
- Anisokenia testing.
- Optical Coherence Tomography (OCT) changes.
- Metamorphopsia according to the patient symptoms.
- Visual acuity (ETDRS 12 months post intervention)

- Metamorphopsia questionnaire^[12]_[SEP]

(viii) Recruitment plan

Recruitment will begin after Research Ethics Board approval has been granted and will continue until the required number of patients are enrolled and have completed the study. Patients visiting the retina clinic with primary RRD will be given the option to participate if they meet the criteria. Based on our clinic's routine volume, we anticipate recruiting approximately 4 patients per sub-study per week, with complete recruitment over a 12-month period. Each patient will be followed for 12 months.

(ix) Screening Procedures

Retinal Displacement after scleral buckle vs pars plana vitrectomy with scleral buckle for primary rhegmatogenous retinal detachment – Protocol # 18-085, version 1, 1/17/2018

Patients will be screened by the investigators in the same manner as standard patients. The tests to be performed are typically used for diagnosis and follow-up of retinal detachment: best-corrected Snellen visual acuity assessment, slit-lamp exam, tonometry, fundoscopy, and Optical Coherence Tomography (OCT) at every visit. ETDRS visual acuity (ETDRS - 'Early treatment of Diabetic Retinopathy Study' – this study defined a method of visual acuity assessment that has become the gold standard for use in eye research) will be assessed at 12 months after the treatment for RRD.

Assessment of Clinical Parameters:

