The following clinical data will be obtained from each patient: age, gender, extent of the detachment (quadrants), duration of subjective symptoms (days), vitreous status (presence/absence of vitreous hemorrhage), macular status (attached/on or detached/off), the location of main retinal tears (fundus sketch), refractive power (emmetropic, hyperopic, myopic <6 or > 6 diopters, lens status (phakic or pseudophakic) and medications in use.

(x) Sample size

Sample sizes were calculated to appropriately power the study. A total sample size of 40 subjects with macula-off detachments undergoing scleral buckles will be recruited. A second group of 40 subjects with macula-off retinal detachments undergoing combined vitrectomy and scleral buckle placement will also be recruited. Anticipating a dropout rate of 20%, we calculated a total of 100 patients in the entire study.

IV. Data management

Initial data collection (clinical examination findings, visual acuity, and questionnaire data) will take place in a paper format. Subsequently, this data will be transferred to a digital database (Microsoft Excel). Paper data will be stored in a locked filing cabinet in the principal investigator's office and away from the study data, and will be destroyed once digital data entry has taken place. The digital spreadsheet will be held on a password protected computer in a locked room, and an encrypted memory stick.^[1] At recruitment, each patient's name and date of birth will be obtained to facilitate onward administration of follow-up appointments and safety monitoring and stored on a face sheet (master linking log). The face sheets will be stored in a locked filing cabinet, away from the study data. Each patient will be allocated a unique study identification number, which will be used to label all paper and digital data pertaining to that patient. The face sheets (master linking log) and all paper/electronic data will be destroyed once publication takes place. The de-identified study data will be destroyed five years after publication has taken place.

V. Consent:

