Written, informed consent for imaging and sensory testing as part of the study will be obtained from each participant. Important: the clinical care of the patient will not be affected by the patient's participation or non-participation in this study of post-surgery imaging and sensory testing. Given that 12-month followup can be problematic for patients who live a great distance from the study sites, a 20% dropout rate is anticipated. There is no charge to the patient for the sensory testing, which is the only element that differs from standard care.

On no occasion should consent be obtained by the treating physician or study investigator.^[17] During working hours: The study will be introduced to the patient by the examining physician. Interested patients are directed to Research Technician who will obtain informed consent.

Late evenings / weekends: Informed consent may instead be obtained by the vitreoretinal surgery fellow (assuming that they are not the treating physician and will not be involved in the patient's surgery). The resident/fellow will be familiar with both interventions (SB and PPV+SB), the nature of the study and trained to the consent discussion and obtaining written informed consent. As retinal detachments are usually unilateral conditions, patients can still read the informed consent. If the patient has any bilateral visual impairment, a witness, usually being the accompanying relative of the patient or a staff member not involved in the study, will also be present.

VI. Data Analysis:

Continuous data: Data will be checked for normality.^[18] Normal data will be compared using a non-paired t-test. Non-normal data will be compared using non parametric tests. Categorical data: Chi squared test. Coefficients with 95% confidence intervals will be reported. A p-value of 0.05 will be considered for statistical significance. Data will be analyzed using SPSS (SPSS Inc., Chicago, IL). Per protocol analysis will be used.

VII. Safety Monitoring Plan

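### The surgeon chooses the operation, yet every comparison named in Section VI is unadjusted, so case mix alone could produce an apparent benefit of scleral buckling

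*Protocol*

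**What the plan says.** Section III(v) of the protocol describes allocation: "Patients are not randomized to the procedure, rather the procedure is chosen by the surgeon in the best interests of the patient". The Background (Retinal detachment) adds that "The choice of which procedure to perform depends on the clinical examination" and on the surgeon's discretion. The Background on interventions says of PPV+SB that "this is used commonly in treatment of larger or more complex detachments".

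The hypothesis in Section III(i) is that "scleral buckling alone may cause less retinal displacement and less visual distortion" than other methods. The primary outcome in Section III(vii) is "retinal displacement by the presence of retinal vessels printing on FAF imaging", which is a yes/no finding.

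Section VI sets the analysis: "Normal data will be compared using a non-paired t-test. Non-normal data will be compared using non parametric tests. Categorical data: Chi squared test". It also promises coefficients with 95% confidence intervals but names no model and no covariate. Under Assessment of Clinical Parameters, Section III(ix) lists the baseline data to be collected. These include extent in quadrants, days of symptoms, vitreous status, tear location, refraction and lens status. No analysis stated in the protocol uses any of them.

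**The concern.** The protocol itself describes confounding by indication: the features of the eye that lead a surgeon to add vitrectomy may also affect how far the retina shifts. Because the primary outcome is binary, the test that Section VI assigns to it is a crude chi-squared test. The t-test and non-parametric tests for the other outcomes are unadjusted too.

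A crude comparison is a valid description of what happened to the two groups. It cannot separate the operation from the eyes that received it. If larger or more complex detachments displace more, the resulting bias favours SB, which is the direction of the hypothesis. A significant crude result would then not by itself support the claim that SB causes less displacement.

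**Working it through.** **The plan's own figure.** Section III(x) asks for 40 eyes per group and allows 20% dropout: 80 / (1 − 0.20) = 100, which matches the stated total. The protocol gives no effect size, event rate or power from which the 40 per group could be reproduced.

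**Inputs from the protocol.** 40 evaluable eyes per group and a 5% significance level (taken as two-sided, since the protocol does not say). The only available anchor for the event rate is a cited vitrectomy series in which "35.2% of patient showed signs of retinal displacement". That series represents neither study group.

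**Assumptions not in the protocol.** There is no true effect of the operation. A yes/no large/complex feature raises displacement and is more common in the PPV+SB group. Its prevalence and strength are varied.

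**Formula.** Crude rate in a group = f × p(large) + (1 − f) × p(small), where f is the share of large/complex eyes. For example, with f = 30% in SB and 60% in PPV+SB, and displacement of 50% in large and 20% in small detachments:

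- SB: 0.3 × 0.5 + 0.7 × 0.2 = 0.29
- PPV+SB: 0.6 × 0.5 + 0.4 × 0.2 = 0.38

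The rejection probability of the Pearson chi-squared test (no continuity correction) was found by exact enumeration of the two binomial distributions with n = 40 each. The last column is the rejection rate when the feature is adjusted for. It comes from 10,000 simulated studies per scenario, using Firth-penalised logistic regression with treatment, the feature and two unrelated covariates.

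| Scenario | Large/complex, SB vs PPV+SB | Displacement, small vs large | Crude rate, SB vs PPV+SB | Crude test rejects | Adjusted test rejects |
|---|---|---|---|---|---|
| Balanced | equal | – | 35.2% vs 35.2% | 4.9% | – |
| Mild (odds ratio 2) | 40% vs 60% | 27.4% vs 43.0% | 33.6% vs 36.8% | 5.9% | 4.1% |
| Moderate (odds ratio 4) | 30% vs 60% | 20% vs 50% | 29% vs 38% | 13.3% | 3.7% |
| Moderate (odds ratio 4) | 20% vs 70% | 20% vs 50% | 26% vs 41% | 29.0% | 3.2% |
| Strong (odds ratio 6) | 20% vs 70% | 20% vs 60% | 28% vs 48% | 46.0% | 3.0% |
| Strong (odds ratio 6) | 20% vs 80% | 16.4% vs 54.0% | 23.9% vs 46.5% | 56.5% | 2.8% |

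In the moderate and strong scenarios at least 98% of the crude rejections favour SB.

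**Second check.** A separate grid kept the overall rate at 35% and used a Cochran-Mantel-Haenszel test stratified by the feature. The stratified test stayed at 4.8% to 5.3% throughout. The crude test ran from 6.5% to 62.0% once the groups were imbalanced.

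**Precision after adjustment.** In the five confounded scenarios, in table order, the ratio of adjusted to crude standard error (log odds) was 1.07, 1.15, 1.27, 1.31 and 1.39.

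**Room for covariates.** At an assumed 35.2%, 80 × 0.352 = 28.2 events. Treatment plus three covariates leaves 28.2 / 4 = 7.0 events per parameter. Adding one site indicator leaves 28.2 / 5 = 5.6.

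**The case against.** The strongest objection is that covariate models are commonly left to the statistical analysis plan, which is not at hand. On this view the promise of coefficients may already signal a regression, so a request for clarification would be enough. The ambiguity is real, and the text should say what the coefficients are. But Section VI does not leave the method open. It names the tests, the significance level, the software and the analysis set, and every test it names is a crude comparison that does not suit surgeon-chosen treatment.

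A second objection is that the mechanism is assumed. The protocol does not say that size or complexity affects displacement. Its remark on PPV+SB describes general practice rather than these sites, and entry is already restricted to macula-off primary detachments without other structural retinal pathology. All of that stands, and it is why the bias is called possible rather than likely. The entry criteria narrow the case mix, but they do not balance extent, duration or lens status between the groups.

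Third, the moderate and strong scenarios use odds ratios of 4 and 6, while the one with an odds ratio of 2 shows almost no inflation. This is also fair: the percentages illustrate a range and do not estimate the bias in this study.

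Last, complexity as such is not recorded and extent is only a proxy. The adjusted results above assume the confounder is measured without error and modelled correctly, so they are optimistic. Adjustment reduces the problem without removing it.

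**Conclusion.** The concern holds. The protocol states that treatment is chosen by the surgeon, says that PPV+SB is commonly used for larger or more complex cases, and then fixes only unadjusted tests for a hypothesis worded causally. With no true effect, the false-positive rate of the primary test ranges from 5.9% to 56.5% across the confounded scenarios in the table, against 4.9% with balanced groups.

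Those figures rest on assumed imbalance, assumed strength of the case-mix effect and an event rate near 35%, none of which the protocol gives for these two groups. The study remains sound as description. The point should be fixed before analysis, because a significant crude difference could not carry the hypothesis.

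**What to change.** Reword Section VI as follows:

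- **Primary comparison.** Compare presence of retinal vessel printing with adjustment for extent in quadrants, symptom duration and lens status, and for site if numbers allow. Name one effect measure in advance (risk difference or odds ratio) and report it with a 95% confidence interval.
- **Method.** Name one in advance: a penalised logistic model, or a propensity score built from the same covariates. If SPSS, the named package, cannot fit the penalised model, use the propensity score.
- **Other outcomes.** Apply the same covariate set to the M-CHARTS and aniseikonia results.
- **Crude tests.** Keep them as supportive, and state what the coefficients refer to.
- **Conclusion.** Word it as an adjusted association and acknowledge residual confounding.

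The cost is redrafting and a little more analysis; no new patients, visits or data are needed. About 28 events support only a few covariates, so the list must stay short and be fixed before the outcomes are seen. Precision is the main price: the simulated standard errors were 7% larger under mild confounding, 15% to 27% under moderate and 31% to 39% under strong. Confounding by features that are not recorded would remain.
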